8.7.6 Pregnancy

There is no information about the effects that AVT05 could have on the development of the fetus in humans. Therefore, it is important that WOCBPs and participants' partners do not become pregnant until at least 6 months after IP administration and agree to use adequate contraception during this period.

Details of all pregnancies in WOCBPs and participants' partners (after obtaining the necessary signed informed consent from the pregnant partner directly) will be collected via a Pregnancy Report Form from the time of IP administration until at least 11 weeks after IP administration. Since this is a single dose study, participants who become pregnant during the study will be encouraged to remain in the study and will be followed for safety up to EoS visit. Only those follow-up procedures that would not expose the participant to additional undue risk will be performed.

The PI or designee will record pregnancy information on a Pregnancy Report Form and submit it to the Sponsor and/or designee within 24 hours of the site's awareness of the pregnancy. The procedures for completing and transmitting pregnancy reports and contact information for pregnancy reporting can be found in the Pregnancy Report Form.

The pregnant participant or partner will also be followed up to determine the outcome of the pregnancy, including spontaneous or voluntary termination. The PI or designee will collect follow-up information on the pregnant participant or partner and the child (including details of

the birth, and the presence or absence of any birth defects, congenital abnormalities, or maternal and/or newborn complications) and the information will be forwarded to the Sponsor. Generally, the follow-up period for a pregnancy will be deemed to have ended when the health status of the child has been determined on its birth. Any termination of the pregnancy will be reported regardless of fetal status (presence or absence of anomalies) or indication for the procedure.

While pregnancy itself is not considered to be an AE or SAE, hospitalizations for complications during pregnancy, or if the outcome of the pregnancy meets the criteria of an SAE (eg, spontaneous abortions, fetal death, stillbirth, congenital anomalies [including those in an aborted fetus], ectopic pregnancy) or elective termination of a pregnancy will be reported as an SAE (Sections 8.7.3 and 8.7.5).

8.7.7 Adverse Events of Special Interest

An adverse event of special interest (AESI) is an AE (serious or nonserious) of scientific and medical concern specific to golimumab, for which ongoing monitoring is required. Such AESIs may require further investigation to characterize and understand them. The AESIs for this study encompass all relevant warnings and precautions from the Simponi Product Information and include:

- Serious infections, including invasive fungal infections. These include:
 - o Active tuberculosis, including reactivation of latent tuberculosis.
 - o Invasive fungal infections including histoplasmosis, coccidioidomycosis, candidiasis, aspergillosis, blastomycosis, and pneumocystosis.
 - O Bacterial (including sepsis and pneumonia), viral, and other infections due to opportunistic pathogens, including *Legionella* and *Listeria*.
 - Hepatitis B Reactivation.
- Malignancies, especially lymphoma.
- Hypersensitivity reactions, including anaphylaxis (details in Section 8.7.7.1) and angioedema
- Autoimmune disorders: lupus-like syndrome.
- Demyelinating disorders: new onset or exacerbation of clinical symptoms and/or radiographic evidence of central nervous system demyelinating disease, including multiple sclerosis, optic neuritis, peripheral demyelinating disease, including Guillain-Barré syndrome.
- Congestive Heart Failure:
 - o worsening congestive heart failure (CHF): New York Heart Association (NYHA) Class 1 which became Class 2/3/4, or NYHA Class 2 which became Class 3 or 4
 - new onset CHF

• Local injection site reactions: pain, tenderness, erythema/redness, and induration/swelling (details in Section 8.6.6). In addition, pruritus/itching, hematoma/ecchymosis/bruising will be considered as injection site reactions.

While these events are noted to be of special interest, they will be reported and assessed in the same manner as standard AEs (unless seriousness criteria are met).

8.7.7.1 Anaphylaxis

Anaphylaxis may be defined when any 1 of the following 3 criteria are fulfilled:

- 1. Acute onset of an illness (minutes to several hours) with involvement of the skin, mucosal tissue, or both (eg, generalized hives, pruritus, or flushing, swollen lips-tongue-uvula), with at least 1 of the following:
 - a) Respiratory compromise (eg, dyspnea, wheeze-bronchospasm, stridor, reduced peak expiratory flow, hypoxemia)
 - b) Reduced BP or associated symptoms of end-organ dysfunction (eg, hypotonia [collapse], syncope, incontinence)
- 2. Two or more of the following that occur rapidly after exposure to a likely allergen for that participant (minutes to several hours):
 - a) Involvement of the skin-mucosal tissue (eg, generalized hives, itch-flush, swollen lips-tongue-uvula)
 - b) Respiratory compromise (eg, dyspnea, wheeze-bronchospasm, stridor, reduced peak expiratory flow, hypoxemia)
 - c) Reduced BP or associated symptoms (eg, hypotonia [collapse], syncope, incontinence)
 - d) Persistent gastrointestinal symptoms (eg, crampy abdominal pain, vomiting)
- 3. Reduced BP after exposure to known allergen for that participant (minutes to several hours): systolic BP <90 mm Hg or >30% decrease from the participants' baseline.

8.8 Immunogenicity Assessments

Venous blood samples (8 mL per sample) will be collected from all participants at the time points specified in Table 2 for the measurement of ADAs to golimumab in serum at a central laboratory. Blood samples will be collected either by direct venipuncture (any suitable vein) or via an indwelling cannula inserted in a vein (depending on the time point). The actual date and time (24-hour clock time) of each sample, including the reason for any samples not collected, will be recorded in the eCRF. Instructions for the collection and handling of biological samples, including details for sample collection, labeling, storage, and shipping will be provided in the Laboratory Manual.

For the immunogenicity assessments, serum samples will be screened for antibodies binding to golimumab in AVT05, US-licensed Simponi, and EU-approved Simponi, and the titer of confirmed positive samples will be reported. Antibodies will be further characterized and/or

evaluated for their ability to neutralize the activity of the IP. All samples collected for detection of antibodies to golimumab will also be evaluated for golimumab serum concentration to enable interpretation of the antibody data.

The immunogenicity assessments will be performed using a validated immunoassay method. Full details of the bioanalytical methods will be described in a separate Bioanalytical Report.

8.9 Inflammatory Cytokine Pharmacodynamic Assessments

For the ex-vivo pharmacodynamic assessments, venous blood samples (4 mL) were collected in lithium-heparin tubes from 45 participants (15 per group) for the measurement of IL-8 levels using an ex-vivo TNF-α stimulation assay at the time points specified in Table 2.

NOTE: As of Protocol Version 4.0, the analysis of the samples collected for the ex-vivo pharmacodynamic substudy will not be performed. The collected samples will be destroyed.

8.10 Residual Samples for Future Scientific Research

With participant consent, residual serum samples will be stored and may be used for the assessment of pharmacodynamics that could help to evaluate their association with observed clinical responses to AVT05. Additional biomarkers may be identified during or after the study and be considered for assessment in the future.

Participants may withdraw consent for use of biorepository samples at any time, as described in the ICF. Samples will be shipped and stored according to instructions in the Laboratory Manual. The samples may be stored for a maximum of 2 years (or according to local regulations) following the last participant's last visit for the study at a facility selected by the Sponsor.

8.11 Genetics

Genetic parameters are not evaluated in this study.

8.12 Health Economics/Medical Resource Utilization

Health economics/medical resource utilization parameters are not evaluated in this study.

9.0 STATISTICAL CONSIDERATIONS

9.1 Statistical Hypotheses

The following statistical hypotheses will be tested to demonstrate the PK similarity of AVT05, US-licensed Simponi and EU-approved Simponi in terms of C_{max} and AUC_{0-inf}.

• The null hypothesis is:

H0: $GM_T/GM_R \le 80\%$ or $GM_T/GM_R \ge 125\%$

• The alternative hypothesis is:

H1: $80\% < GM_T/GM_R < 125\%$

where GM_T and GM_R denote the geometric mean of PK parameter (eg, C_{max} and AUC_{0-inf}) in the Test and Reference groups, respectively. Following pairwise comparisons will be performed for each primary PK parameter:

- AVT05 (T) vs. US-licensed Simponi (R)
- AVT05 (T) vs. EU-approved Simponi (R)
- EU-approved Simponi (T) vs. US-licensed Simponi (R)

9.2 Sample Size Determination

The primary PK endpoints for this PK study are C_{max} and AUC_{0-inf}. Sample size calculations were performed using SAS Version 9.4, and were based on PK parameter summary data from Ling and Lyn (2010). Based on this study, the inter-participant coefficient of variation (CV%) is assumed to be 35.0% for AUC_{0-inf} and 37.7% for C_{max}.

The assessment of PK similarity will be based on the 90% confidence interval (CI) for the geometric mean ratio (GMR) between 3 treatment groups will be calculated for all 3 pairwise comparisons (AVT05 to US-licensed Simponi, AVT05 to EU-approved Simponi, and EU-approved Simponi to US-licensed Simponi) for both primary endpoints AUC $_{0-inf}$ and C_{max} . The PK similarity will be demonstrated if the 90% CIs of the GMR for both AUC $_{0-inf}$ and C_{max} lie entirely within the prespecified margins of 80% and 125% (when the ratio is expressed as a percentage) in all pairwise treatment comparisons.

Assuming a true GMR of 95%, 101 evaluable participants per treatment group will provide a power of 95.5% for each individual comparison of C_{max} and a power of 97.4% for each individual comparison of AUC_{0-inf}. Considering a non-evaluable rate of 10%, the total sample size of 336 participants (112 per treatment group) will provide an overall study power of 80.5%.

Of the 336 participants, at least 10% (33 participants, 11 per group) participants of Japanese origin are planned to be enrolled.

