9.4.6 Statistical Analysis for PK Similarity

The primary PK parameters for the demonstration of PK similarity between AVT05 and the Simponi reference products will be C_{max} and $AUC_{0\text{-inf}}$. The statistical analysis will be performed using an ANCOVA model on the logarithmic scale (ie, using natural log-transformed values of C_{max} and $AUC_{0\text{-inf}}$) including treatment group as fixed effect and with gender as factor and body weight at baseline as continuous covariate.

Point estimates (geometric means and GMRs) will be calculated by back transforming the LS means of the natural log-transformed values of C_{max} and AUC_{0-inf} and the difference in the LS

means. The PK similarity of AVT05 versus US-licensed Simponi, AVT05 versus EU-approved Simponi, and EU-approved Simponi versus US-licensed Simponi will be demonstrated if, for each pairwise comparison, the 90% CIs for the GMRs of the primary endpoints are entirely contained within the equivalence margin of 80% to 125% (when the ratio is expressed as a percentage). Other exploratory analyses of PK similarity by subgroups based on the randomization strata, ADA status, and NAb status may be performed if appropriate.

Differences in drug protein concentration have been identified between AVT05 (101.0 mg/mL), US-licensed Simponi (94.7 mg/mL), and EU-approved Simponi (91.4 mg/mL). Therefore, the PK similarity analysis using PK parameters adjusted by protein content will be performed as a sensitivity analysis.. Further details will be provided in the SAP.

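### The overall power of 80.5% in Section 9.2 assumes a GMR of 95% for all three pairs, which three arms cannot have; a coherent reading gives about 87–92%

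*Combined protocol and SAP*

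**What the plan says.** Protocol Section 9.2 takes inter-participant CVs of 37.7% for Cmax and 35.0% for AUC0-inf. It then says: "Assuming a true GMR of 95%, 101 evaluable participants per treatment group will provide a power of 95.5% for each individual comparison" of Cmax, with 97.4% given as the counterpart for AUC0-inf. After a 10% allowance for non-evaluable participants, it concludes that "the total sample size of 336 participants (112 per treatment group) will provide an overall study power of 80.5" per cent.

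Similarity is claimed only if the 90% confidence intervals for both endpoints "lie entirely within the prespecified margins of 80% and 125" per cent "in all pairwise treatment comparisons". Section 9.1 lists three pairs: AVT05 against each reference, and EU-approved against US-licensed Simponi. Success therefore means passing six equivalence tests.

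Section 9.2 does not say how 80.5% was obtained, which pairs the 95% ratio applies to, or what dependence between the tests was assumed.

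**The concern.** The overall power is the only figure given for the rule that decides the study, so it is the figure that justifies 336 participants. It coincides with the product of the six single-test powers. That product would be right only if all three pairs had a true ratio of 95% and the six tests were independent.

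The ratios of three arms are linked, so the first condition is impossible. Shared arms and shared participants rule out the second. If the figure was built this way, it describes no possible state of the three products, and a reader cannot tell which true ratios the study is powered for. That choice matters, because joint power depends strongly on it.

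**Working it through.** **Inputs.** From Section 9.2: CV 37.7% (Cmax) and 35.0% (AUC0-inf), true GMR 0.95, 101 evaluable per arm, 90% CI (one-sided 5% per test), margins 0.80 to 1.25, both endpoints in all three pairs. Not in the documents, so assumed: the Cmax–AUC0-inf correlation, varied from 0 to 1.

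**1. Single-test powers.** Log-scale SD = √ln(1 + CV²): √ln(1 + 0.377²) = 0.3645 for Cmax and √ln(1 + 0.35²) = 0.3399 for AUC0-inf. Exact two-one-sided-tests power at GMR 0.95 with 101 per arm is 0.9547 and 0.9735 with two-arm degrees of freedom, or 0.9551 and 0.9738 with three-arm pooling. The stated 95.5% and 97.4% reproduce and are not in dispute.

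**2. The overall figure.** (0.955 × 0.974)³ = 0.8048, which rounds to the stated 80.5%. From unrounded powers the product is 80.3% (two-arm) or 80.4% (pooled). At 112 per arm it would be about 86.6%, so the stated figure refers to 101 evaluable. That the product was the method is an inference from this match.

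**3. Three ratios of 0.95 are impossible.** On the log scale, ln(AVT05/US) = ln(AVT05/EU) + ln(EU/US). If two of the three log ratios have size δ = |ln 0.95|, the third has size 0 or 2δ. The third ratio is therefore 1.00, or 0.95² = 0.9025, or 1/0.9025. It is never 0.95 or its inverse.

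**4. A bound that needs no correlation.** Take two pairs at 0.95 and the third at 1.00. Power at ratio 1.00 is 0.9929 (Cmax) and 0.9973 (AUC0-inf). The failure probabilities sum to 2 × (4.53 + 2.65) + (0.71 + 0.27) = 15.34%. Joint power is therefore at least 84.7% under any dependence, so 80.5% cannot occur in this case. Under independence it is 0.9547² × 0.9735² × 0.9929 × 0.9973 = 85.5%.

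**5. Joint simulation.** Shared arm means, correlated endpoints, three-arm pooled variance, 101 per arm, 400,000 trials per case (Monte Carlo standard error about 0.05 points). Joint power in %, by Cmax–AUC correlation:

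| True ratios | 0 | 0.5 | 0.8 | 0.95 | 1 |
|---|---|---|---|---|---|
| AVT05 at 0.95 to both references | 87.2 | 88.3 | 89.8 | 91.1 | 91.6 |
| AVT05 = EU, both at 0.95 to US | 87.2 | 88.3 | 89.8 | 91.1 | 91.7 |
| AVT05 = US, EU differing by 0.95 | 87.1 | 88.2 | 89.8 | 91.1 | 91.6 |
| AVT05/US at 0.95, EU midway | 90.0 | 90.9 | 92.1 | 93.1 | 93.5 |

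An independent run of the first two rows (300,000 trials per case, pooled and pairwise variance) gave 86.9% to 91.7%.

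**6. Where the gap comes from.** Correcting the third ratio alone moves 80.5% to 85.5%, about 5 points. Allowing for dependence adds 87.2 − 85.5 = 1.7 to 91.6 − 85.5 = 6.1 points.

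**7. In sample-size terms.** With AVT05 at 0.95 to both references, joint power near 80.5% needs about 90 evaluable per arm at correlation 0 (81.1% at 90, 79.7% at 88), 86 at correlation 0.5 (80.4%) and 82 at correlation 0.8 (80.5%). The plan has 101.

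**8. The other coherent reading.** If two steps of 0.95 form a chain, one pair is at 0.9025 and joint power is about 57% to 73%. That pair alone would have about 76% (Cmax) and 81% (AUC0-inf) power, not the 95.5% and 97.4% that Section 9.2 gives for each comparison.

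**The case against.** The strongest reply is that nothing follows from the error. A product of marginal powers is a simple planning approximation. Here it lies below every joint power computed with no pair further from 1 than 0.95, and the sample size, margins, success rule and analysis model all stay as they are. It could be labelled a conservative approximation and left. The point about consequences stands, and it limits the weight of the finding. It does not make the figure right: Section 9.2 presents 80.5% as the power of the study, not as a lower bound.

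A second reply is that 87–92% is itself a choice of scenario. Section 9.2 states only one ratio, and the limit that no pair lies beyond 0.95 is inferred from the power claimed for each comparison. This is fair. With EU midway, joint power is 90% to 93.5%, so the gap is about 10 to 13 points. With all ratios at 1.00 it is 97% to 98%. The chain gives 57% to 73%. A set with one pair somewhere between 0.95 and 0.9025 could give 80.5%, but that pair would not have the stated single-test power. The spread is a reason to state the ratios.

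A third reply is that the method is inferred, and that the product of unrounded powers is 80.3% or 80.4%. An explanation elsewhere in the protocol cannot be excluded. The conclusion does not depend on the inference: with two pairs at 0.95 and one at 1.00, the bound of 84.7% excludes 80.5% however it was computed.

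**Conclusion.** The concern holds. The single-comparison powers are correct, but the overall 80.5% does not follow from them for a three-arm study. If two pairs differ by 0.95 and the third is at 1.00, which is the reading that keeps the stated power for every comparison, joint power at 101 evaluable per arm is about 87% to 92%. The stated figure is then about 7 to 11 points too low.

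This rests on the CVs in Section 9.2, log-normal data, no gain from the covariates in the Section 9.4.6 model (the plan's own single-test powers reproduce without any), and an endpoint correlation anywhere from 0 to 1.

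The error is conservative. On this reading the sample size is adequate, and no analysis or decision rule is affected. It should be corrected because it is the stated justification for the sample size and does not identify the true ratios to which it applies.

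**What to change.** In Section 9.2:

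- State the assumed true ratio for each pair, for example AVT05 at 0.95 to each reference with EU/US at 1.00.
- State the assumed Cmax–AUC0-inf correlation, or a range.
- Replace 80.5% with the joint power simulated under those assumptions (about 87–92% for the example), and say that it was simulated.

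Optionally, add a sensitivity case with one pair near 0.90 or its inverse, marked as outside the main assumption. The protein concentrations in Section 9.4.6 give ratios of 101.0/91.4 = 1.105 (AVT05/EU), 101.0/94.7 = 1.067 (AVT05/US) and 91.4/94.7 = 0.965 (EU/US). If exposure scaled fully with protein content, which is an assumption, joint power on the unadjusted parameters would be about 59% to 74%. This case is separate from the correction above.

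The cost is one or two sentences and a short simulation. No extra participants are needed and the analysis does not change.

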9.3 Analysis Populations

Table 7 Analysis Populations

Analysis Population	Description
Entered Population	All participants who sign the ICF.
Randomized Population	All participants who are randomized into this study. Participants will be analyzed according to their randomized treatment, regardless of which treatment the participant receives.
Safety Population	All randomized participants who receive any amount of the IP. Participants will be analyzed according to the treatment they receive, if this differs from that to which the participant is randomized.
Pharmacokinetic Population	All randomized participants who receive any amount of the IP and have at least 1 evaluable PK parameter. Participants will be analyzed according to the treatment they receive, if this differs from that to which the participant is randomized. Participants with dosing deviations that could potentially affect the PK profile will be excluded from the PK Population, at the discretion of the blinded pharmacokineticist prior to analysis.
Immunogenicity Population	All randomized participants who receive any amount of the IP and have at least 1 evaluable postdose immunogenicity result (ie, positive or negative for presence of ADAs). Participants will be analyzed according to the treatment they receive, if this differs from that to which the participant is randomized.

Abbreviations: ADA = antidrug antibody; ICF = Informed Consent Form; IP = investigational product; PK = pharmacokinetics.

9.4 Statistical Analyses

The following sections describe the statistical analysis as it is foreseen when the study is being planned. A detailed Statistical Analysis Plan (SAP) will be developed and finalized before database lock and will describe the participant analysis populations to be included in the analyses, and procedures for accounting for missing, unused, and spurious data. The SAP will also provide the format of listings, tables, and figures to be provided for completion of the Clinical Study Report (CSR). Any deviations from the SAP will be presented in the final CSR. This section is a summary of the planned statistical analyses of the primary and secondary endpoints.

All statistical analyses, summaries, and listings will be performed using SAS software (Version 9.4 or higher) (SAS Institute, Inc., Cary, North Carolina, USA).

In general, data will be presented by treatment group. Data for all study participants combined will also be presented when appropriate. Individual participant data will be presented in listings by randomization strata.

The following descriptive statistics will be used as applicable to summarize the study data unless otherwise specified:

- Continuous variables: sample size (N), number of non-missing counts (n), mean, SD, median, minimum (min), and maximum (max). The CV%, geometric mean, and geometric CV% will be presented for PK parameters, where applicable.
- Categorical variables: frequency counts and percentages.

Baseline will be defined as the last available, valid, non-missing assessment (scheduled or unscheduled) prior to dosing. Only data from protocol-scheduled visits/time points will be included in the summary tables and figures. All data, including those from unscheduled visits/time points will be included in the listings.

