8.7.1.3 Recording of Adverse Events Based on Other Safety Assessments

For protocol-specified laboratory parameters, any laboratory abnormality that is new in onset or which has worsened in severity or frequency from the baseline condition and meets one of the following criteria will be recorded on the AE pages of the eCRF if not captured as part of an overarching diagnosis (eg, hemoglobin of 8 g/dL captured as part of anemia):

- Requires therapeutic intervention or additional diagnostic tests.
- Has accompanying clinical symptoms or signs.
- Is judged by the PI as clinically significant.

Additionally, any abnormalities in protocol-specified laboratory parameters that meet the CTCAE Grade \geq 3 criteria are considered to be clinically significant and will be recorded as AEs.

Any clinically significant deterioration in vital signs, ECGs, and physical examinations as compared with baseline should also be recorded as AEs.

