9.4.7.2 Local Injection Site Reactions

Local injection site reactions will be listed and summarized using frequency counts and percentages by treatment group and for all participants: by most severe reaction (pain,

tenderness, erythema/redness, induration/swelling, and other reactions) and by each reaction for each scheduled time point, and intensity grade (including Grade ≥1). The worst postbaseline injection site reaction intensity grade observed at any time (scheduled or unscheduled) during the study will also be presented.

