9.4.7.3 Clinical Laboratory Evaluations

Observed values and change from baseline for clinical laboratory data (hematology, coagulation, and clinical chemistry) will be listed and summarized using descriptive statistics at each protocol-specified time point by treatment group. Separate listings will be produced for all participants with at least 1 out-of-range or abnormal clinical laboratory result.

Shifts in the PI's evaluation of laboratory parameters (Normal, Abnormal NCS, Abnormal CS) from baseline to each postbaseline protocol-scheduled time point will be summarized by treatment group, using frequency tabulations.

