9.4.7.4 Vital Signs, Electrocardiograms, and Physical Examinations

All vital signs and ECG data and the PI's evaluation of abnormal physical examination findings will be presented in data listings.

In addition, observed values and change from baseline for vital signs and ECG data will be summarized at each protocol-specified time point, by treatment group. Shifts in the PI's evaluation of the results (Normal, abnormal NCS, Abnormal CS) from baseline to each postbaseline protocol-scheduled time point will also be summarized by treatment group using frequency tabulations.

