10.2 Clinical Laboratory Tests

- The tests detailed in Table 8 will be performed locally as per the time points specified in the Schedule of Assessments (Table 1).
- Protocol-specific laboratory-related requirements for inclusion or exclusion of participants are detailed in Section 5.0 of the protocol.
- Additional tests may be performed at any time during the study as determined necessary by the PI or required by local regulations or the local laboratory SOPs.
- The PIs (or medically qualified delegate) must document their review of each laboratory safety report.
- Laboratory/analyte results that could unblind the study will not be reported to study sites or other blinded personnel until the study has been unblinded.

Table 8 Protocol-required Safety Laboratory Assessments

Laboratory Assessments	Paramete	ers
Hematology	Red blood cell count	White blood cell count with differential
	Hemoglobin	
	Platelet Count	
Coagulation	Prothrombin time	International normal ratio
	Activated partial thromboplastin time	
Clinical Chemistry ^a	Albumin	Creatinine
	Albumin/Globulin Ratio	CRP
	ALT	GGT
	Alkaline Phosphatase	Globulin
	AST	Glucose
	Bilirubin direct	Lactate dehydrogenase
	Bilirubin indirect	Phosphorus-inorganic
	Bilirubin-total	Potassium
	Urea	Protein-total
	Urea/creatinine ratio	RF
	Calcium	Sodium
	Cholesterol	Triglycerides
	Chloride	Uric acid
	Creatine kinase	HbA1c (at Screening only)
Urinalysis (dipstick)	Protein	pH of freshly voided specimen
	Glucose	Ketones
	Nitrites	
	Microscopy (if clinically indicated)	

Laboratory Assessments	Parameters		
Viral serology	HIV 1 and 2 antibodies	Anti-HBc	
(Screening only)	HBsAg	HCV antibody	
	Anti-HBs		
Fungal test	β-D glucan		
(Screening only)			
COVID-19 test	As per local site, health authority, and Investigator requirements.		
Tuberculosis testing	QuantiFERON®-TB Gold in Tube		
Drugs of abuse	Amphetamines	Benzodiazepines	
(Screening only)	Cannabinoids	Methadone metabolites	
	Cocaine metabolites	Barbiturates	
	Ecstasy (3,4-Methylenedioxymethamphetamine)	Phencyclidine	
	Opioids and opiates		
Alcohol testing	Alcohol breath test using a commercial breathalyzer (Screening only)		
Pregnancy and FSH tests	Serum and urine human chorionic gonadotropin (hCG) pregnancy tests will be done for participants of childbearing potential only. Follicle-stimulating hormone test at Screening (to determine postmenopausal state in participants of non-childbearing potential only)		

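### Laboratory, vital-sign and ECG shift tables have no worst-postbaseline row, so an abnormal value seen only at an unscheduled assessment is summarized by arm only if it is recorded as a TEAE

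*Combined protocol and SAP*

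**What the plan says.** Section 9.4 sets a general rule for displays: "Only data from protocol-scheduled visits/time points will be included in the summary tables and figures". It then says where the rest goes: "All data, including those from unscheduled visits/time points will be included in the listings".

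The shift tables apply the same limit. For the investigator's evaluation of laboratory results (Normal, Abnormal NCS, Abnormal CS), Section 9.4.7.3 plans shifts "from baseline to each postbaseline protocol-scheduled time point will be summarized by treatment group, using frequency tabulations". For vital signs and ECG, Section 9.4.7.4 plans them "from baseline to each postbaseline protocol-scheduled time point will also be summarized by treatment group using frequency tabulations". Neither section adds a row for the worst postbaseline result.

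Injection site reactions are handled differently in Section 9.4.7.2: "The worst postbaseline injection site reaction intensity grade observed at any time (scheduled or unscheduled) during the study will also be presented".

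Unscheduled testing is foreseen. Section 10.2 says: "Additional tests may be performed at any time during the study as determined necessary by the PI". Section 10.4 also allows extra hepatic assessments, Holter monitoring and telemetry.

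There is a second route into the summaries, through adverse events. Under Section 8.7.1.3, a new or worsened abnormality in a protocol-specified laboratory parameter is recorded as an AE if it needs treatment or further diagnostic tests, comes with symptoms or signs, or is judged clinically significant. Values of CTCAE Grade 3 or higher "are considered to be clinically significant and will be recorded as AEs". Clinically significant deterioration in vital signs or ECG is also to be recorded. Section 9.4.7.1 summarizes TEAEs by arm, with separate summaries for clinically significant and for Grade 3 or higher laboratory abnormalities.

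**The concern.** The shift tables are the plan's by-arm display of how laboratory, vital-sign and ECG evaluations moved from baseline. Take a participant who is normal at one scheduled visit, abnormal at an unscheduled test, and normal at the next scheduled visit. That participant is counted as normal throughout. The same abnormal result at a scheduled visit would have been counted. Whether a result reaches the table therefore depends on the kind of visit at which it was found.

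The plan avoids this for injection site reactions and gives no reason for treating the other safety domains differently. At stake is how completely the descriptive safety tables show abnormal findings in each arm. No primary or inferential result is involved.

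**Working it through.** The plan states no figure to reproduce, and the point turns on tabulation rules. The check is to follow each kind of postdose finding that occurs only at an unscheduled assessment through Sections 9.4, 8.7.1.3, 9.4.7.1, 9.4.7.3 and 9.4.7.4.

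| Finding at an unscheduled assessment only | Shift table | TEAE summary by arm | Listing |
|---|---|---|---|
| Laboratory, Grade 3 or higher | No | Yes, automatic | Yes |
| Laboratory, below Grade 3, new or worsened, meeting an AE criterion in Section 8.7.1.3 | No | Yes | Yes |
| Laboratory, abnormal, meeting no AE criterion | No | No | Yes |
| Vital sign or ECG, deterioration judged clinically significant | No | Yes, in the general TEAE tables; no dedicated one | Yes |
| Vital sign or ECG, abnormal, judged not clinically significant | No | No | Yes |

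Three things follow.

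1. **Values in no summary.** Rows three and five reach the listings only. Abnormal NCS is one of the planned shift categories, so these are results that the plan would count if they fell on a scheduled visit. For vital signs and ECG, entry as an AE rests on judgment alone. There is no counterpart to the Grade 3 rule and no dedicated TEAE summary in Section 9.4.7.1, so the gap is widest there.

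2. **Size of the peak.** Even where a TEAE is recorded, Section 8.7.2.1 grades it mild, moderate or severe by clinical judgment. The measured value at an unscheduled assessment is not summarized.

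3. **Ever-abnormal rate.** A table by visit does not say how many participants were abnormal at least once. If *a* participants are abnormal at one visit and *b* at another, the number ever abnormal at the two lies between max(*a*, *b*) and *a* + *b*. With *a* = *b* = 1 and the 112 per group of Section 9.2, that is between 1/112 = 0.9% and 2/112 = 1.8%. This holds even if no unscheduled test is ever done.

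Weight of one case: 1/112 = 0.0089, or 0.9% of a planned arm for one parameter. The denominator in the report will be the Safety Population, which may be slightly smaller. The number of unscheduled assessments is not given, so this is not an estimate of the total effect.

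**The case against.** The strongest reply is that the AE route already catches what matters. Section 8.7.1.3 applies at any visit, and its laboratory criteria are broad. The footnote to Table 8 in Section 10.2 also makes possible Hy's Law results reportable as SAEs. What stays out of the summaries is mostly low-grade, symptom-free and judged not clinically significant, and all of it is listed. Section 9.4.7.3 adds separate listings for participants with any out-of-range or abnormal laboratory result. This stands, and it is why the point is minor. A reader might infer that an unscheduled worst value never enters a summary; Sections 8.7.1.3 and 9.4.7.1 show otherwise.

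A reader might also infer that the omitted values are the most informative ones, or that the tables are biased. The documents do not support this. Unscheduled tests can also be repeats that confirm or refute an earlier result. A by-visit table correctly describes status at that visit, and leaving out discretionary tests keeps testing intensity from driving it. Nothing suggests that such testing would differ between blinded arms.

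A further tempting reading is that the scheduled-only rule contradicts the baseline definition just before it in Section 9.4, which admits unscheduled assessments. The natural reading is a specific definition followed by a general rule for postbaseline displays, so a clarifying clause is enough.

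Injection site reactions are an adverse event of special interest with their own grading scale, so a worst-grade summary for them does not oblige one elsewhere. That is fair: the contrast shows that the plan can make such an exception, not that it erred.

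Finally, Section 9.4 leaves table formats to a detailed SAP. No SAP text on these tables was in the material reviewed, so such a row may already be planned. If so, only the wording of Section 9.4 needs to be aligned with it.

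**Conclusion.** The point holds in a limited form. As written, the laboratory, vital-sign and ECG shift tables omit abnormal results found only at unscheduled assessments, and those results are summarized by arm only when recorded as TEAEs. Three items are in no by-arm summary: unscheduled abnormal values that meet no AE criterion, the size of unscheduled peaks, and the per-participant rate of ever being abnormal.

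The total size is unknown, with each affected participant weighing about 0.9% of a planned arm per parameter. No direction between arms is claimed. The conclusion assumes that Section 8.7.1.3 is applied as written and that the detailed SAP adds no worst-postbaseline row. It is a minor matter of safety presentation, and the PK similarity conclusion does not depend on it.

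**What to change.** Keep the by-visit tables as they are. In Sections 9.4.7.3 and 9.4.7.4, add to each laboratory, vital-sign and ECG shift table a row from baseline to worst postbaseline evaluation, scheduled or unscheduled, by treatment group. The three investigator categories already have a clear order for choosing the worst. In Section 9.4, state that baseline and worst-postbaseline rows are exceptions to the scheduled-only rule.

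The row supplies the missing categories and the ever-abnormal rate. It does not show the numerical size of a peak, which would still be read from the listings.

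The cost is slightly more programming, using data already collected and listed, with no new procedures. The downside is that the row partly reflects how often investigators choose to retest. A footnote to the table should say so, and the by-visit rows beside it remain free of that influence.
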